13.2. Data entry

A double data entry of all data collected during the study will be performed by two independent data entry operators on an interactive mode. Data entry operators will be trained to the study specificities by the data-manager in charge of the study.

All steps of data entry, coding and data handling as well as software used for data entry will be documented by SYLIA-STAT LANCRENON.

Any queries arising after data entry in the database must be answered using DCFs. The Investigator is responsible for resolving any query and must sign every DCF to confirm that the data is accurate.

All electronically issued documents will be identified with the subject number.

13.3. Database lock – individual data listing

Once the database is clean, a blind review will be organized with the Sponsor to check the consistency of the data.

Prior to the database lock, all the following prerequisites will be checked:

- Data entry of all collected data,
- Resolution of all data inconsistencies,
- Validation of data coding (if applicable),
- Proofreading of all non coded texts,
- Blind review performed,
- Determination of protocol deviations,
- Approval of the statistical analysis plan.

After authorization by the sponsor, the database will be locked and a certificate attesting of the lock will be sent to the Sponsor.

13.4. Data transfer

The SAS database will be transferred to the sponsor as a compressed file protected by password.

14. SAMPLE SIZE / STATISTICAL ANALYSIS

A statistical analysis plan (SAP) will be prepared by the SYLIA-STAT LANCRENON and validated by the Sponsor prior to the database lock. Statistical analyses will be performed with SAS® version 9.4 or higher (SAS institute, North Carolina, USA).

14.1. Sample size calculation

The primary objective of this study is to demonstrate the superiority of fla 688977 33 versus Hydréane légère on the total number of lesions at W12.

The following hypotheses, based on previous studies (4) were used for the estimation of the sample size calculation:

- Power $(1 - \beta) = 80\%$
- Two-sided significance level $(\alpha) = 5\%$
- Expected inter-treatment difference (on the changes W12-W0) = 1.15
- Standard deviation = 5.0
- Correlation between the baseline and the endpoint $R^2 = 0.70$

Using the sample size calculation method for covariance analysis (7), the number of evaluable subjects is estimated at 90 by treatment group (180 subjects total).

If we anticipated 10% of drop-out, the total number of subjects required is 200.

14.2. Study population for analysis

Efficacy evaluation will be done on “per protocol” PP population (randomized subjects without Major Deviations) while safety evaluation will be done on “Intent-To-Treat” ITT population (all subjects randomized with at least 1 application of each IP).

* Major deviations will be defined during the blind review

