9.6. Screen failures, subject withdrawals and replacement criteria

Non-included subjects, that is, subjects who have signed informed consent but are removed from the study during the screening process because they do not meet the inclusion/exclusion criteria, are classed as screen failures. Subjects who leave the study after randomisation or assignment to study treatment are classed as withdrawals rather than screen failures, even if the subject had not started the study treatment.

Subjects not completing the study for any reason will be considered as withdrawals and will not be replaced.

Criteria for withdrawal:

1. Subject withdraws consent: subjects will be free to withdraw from the study at any time and for any reason. (In accordance with the Declaration of Helsinki),
2. Adverse event / Serious adverse event: any adverse event that the investigator considers it is not in the subject's best interest to continue,
3. Protocol deviation (after agreement of the Sponsor and/or the investigator),
4. Subject lost to follow-up,
5. Other reasons: other reasons than stated above which requires subject to be withdrawn as:
 - any other situation where, in the opinion of the investigator, continuation of the study would not be in the interest of the subject;
 - Discontinuation of the study by the Sponsor.

The CRF should be completed up to the time of screen failure or withdrawal.

A subject will be considered as "Lost to Follow-up" after 3 phone calls (recorded) and a mail (registered mail with Acknowledgement of receipt) stayed without answer.

All subjects who are prematurely discontinued from the study should have the reason carefully documented by the Investigator/study team in the CRF, final page 'End of study', and, as applicable, on the Adverse Event Form and/or Concomitant Treatment Form.

No follow-up will be planned for the withdrawn subjects.

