10.5. IP accountability, compliance and destruction

Receipt, checking, registration of storage and dispensing of the IP will be carried out in each study centre.

The subjects will record each IP (cosmetic product & drug) application in their daily log. Their compliance with this requirement will be checked by a member of the study team at each visit from a review of the daily log. The number of IP applications will be reported in the CRF in order to compute the compliance at each visit as follow:

Compliance will be expressed by the ratio of the number of applications of the IP actually applied to the theoretical number of IP applications.

The compliance of the cosmetic products should be comprised between 80-120% whereas the compliance of the drug treatment should not be inferior to 75%.

Any deviation from the required IP use regime will be documented in the study report.

At the end of the study, the used and unused IP (cosmetic products) will be checked and then returned to the Sponsor whereas the unused IP (marketed pharmaceutical drug) will be destroyed by each study centre.

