11.4. Prior and concomitant medication

Any topical or systemic therapy used in the 4 weeks prior the Visit 1 will be recorded in the CRF, with the following information:

- name of the drug, type of formulation, and unit strength,
- dose administered,
- start and stop dates,
- reason for treatment.

The following treatments are not allowed:

- isotretinoin treatment within the 6 months prior the Visit 1 and during the study
- surgical/medical procedures on the face (deep cleansing, dermabrasion, peeling, light-therapy, laser...) during the study,
- systemic drugs for more than 3 consecutive days related to antibiotics, anti-inflammatory, corticoids, anti-acneic in the 4 weeks prior the Visit 1 and during the study,
- topical drugs for more than 3 consecutive days related to antibiotics, anti-inflammatory, corticoids, anti-acneic in the 2 weeks prior the Visit 1 and during the study,

Any subject using a concomitant therapy during the study that could interfere with the assessment of the IP will be considered for withdrawal from the study, at the discretion of the investigator.

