14.3. Data description and statistical analysis

Subject disposition

Data from subjects of all defined populations, from subjects who completed the study, and from subjects who withdrew from the study will be summarized by product group using descriptive statistics.

Data from subjects who withdrew from the study will also be summarized by reason for withdrawal using descriptive statistics.

Demographic and Baseline Characteristics

Subjects demographic and baseline characteristics will be summarized by product group using descriptive statistics. For continuous variables, descriptive statistics (n, mean, standard deviation, standard error, median, minimum, and maximum) will be provided. For categorical variables, subject counts and percentages will be provided. Categories for missing data will be presented if necessary.

Efficacy analyses

Analyses will use 2-sided tests at the 5% significance level, except the normality tested at the threshold of 1% (Shapiro-Wilk test).

For all parameters, descriptive statistical tables along with graphics will be performed.

For quantitative parameters (such as clinical counting of cutaneous lesions, sebumetry, corneometry, pHmetry), products will be compared by a covariance analysis with Product and Time as fixed factors, Subject as random factor and value at baseline as covariate (mixed models for repeated longitudinal using SAS® Mixed procedure). The interaction Time x Product will be tested. **Contrasts between products will be evaluated at each time. For the total number of cutaneous lesions, W12 will be considered as the primary contrast.**

Ordinal parameters such as the GEA will be analysed using generalized linear random model for multinomial data (a model for binary data can also be used according to the results of the descriptive analysis), with Subject as random factor, Time and Product as fixed factors and the value at baseline as covariate (SAS® Glimmix Procedure).

All comparisons will be carried out using contrasts. Tests will be followed by a Benjamini-Hochberg adjustment for multiple comparisons.

Data collected [from the efficacy and cosmetic acceptability questionnaires](#) at W12 will be described and compared between products by a chi-square test.

Safety analyses

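### The W12 superiority test is assigned only to the per-protocol set, and no efficacy analysis of all randomised subjects is planned in the supplied text

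*Combined protocol and SAP*

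**What the plan says.** - **Objective.** Section 14.1 says the trial is to "demonstrate the superiority of fla 688977 33 versus Hydréane légère on the total number of lesions at W12". Section 14.3 adds, under the efficacy analyses: "For the total number of cutaneous lesions, W12 will be considered as the primary contrast".
- **Analysis sets.** Section 14.2 assigns efficacy evaluation to the "PP population (randomized subjects without Major Deviations) while safety evaluation will be done on" the set it labels ITT. That set is defined as "ITT population (all subjects randomized with at least 1 application of each IP"), so it is a treated set and not all randomised subjects.
- **Exclusions.** "Major deviations will be defined during the blind review" (Section 14.2). No list of qualifying events is given, and the text does not say whether withdrawal counts.
- **Other sets.** Neither Section 14.3 nor the statistical part of the synopsis (Section 4) names another efficacy set or a sensitivity analysis. Section 14.3 refers to all defined populations only for descriptive subject disposition.
- **SAP.** Sections 13.3 and 14 require a separate SAP before database lock. It is not among the supplied documents.

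**The concern.** Randomisation makes the two groups comparable as allocated. A per-protocol set keeps that protection only if exclusion is unrelated to the combination of arm and outcome. Here it may be related.

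Two likely grounds for a major deviation arise after randomisation. One is compliance: the "compliance of the cosmetic products should be comprised between 80-120% whereas the compliance of the drug treatment should not be inferior to 75" per cent (Section 10.5). The other is a disallowed treatment, such as topical drugs from classes that include "anti-inflammatory, corticoids, anti-acneic in the 2 weeks prior the Visit 1 and during the study" (Section 11.4).

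The product may affect both. Sections 6 and 7.2 set out to show that it improves local tolerance of the drug treatment. If it does, adherence to the drug could differ by arm, and so could membership of the efficacy set. Blind review prevents reviewers from choosing by arm, but it does not prevent exclusions that the product has caused.

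The bias could go either way. Dropping poor adherers may remove poor results. Dropping subjects who used a disallowed anti-acne drug may remove good ones.

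**Working it through.** **1. Reproduce the planned size.** Inputs from Section 14.1: difference 1.15, SD 5.0, R² = 0.70, two-sided 5%, power 80%.

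- Residual SD = 5.0 × √(1 − 0.70) = 2.739.
- n per arm = 2 × [2.739 × (1.960 + 0.842) / 1.15]² = 89.02, rounded up to 90.
- 180 / 0.90 = 200.

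The stated figures reproduce. Power at 90 per arm is 80.4% by the normal formula and 80.0% by noncentral t with N − 3 degrees of freedom. Noncentral t is used below. The 10% drop-out is the only loss allowed for.

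**2. Illustrate the effect of selective exclusion.** The documents give no exclusion rate and no link to outcome, so both are assumed. Each subject has a latent normal exclusion score with correlation r to the W12 residual, and the top fraction p is removed in each arm. The mean residual of those kept moves by −r × 2.739 × λ(p), where λ(p) = φ(a)/(1 − p) and a is the upper-p normal point. This gives λ(0.10) = 0.195 and λ(0.20) = 0.350.

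With 20% of the studied arm and 10% of the comparator arm excluded, the spurious difference is r × 2.739 × (0.350 − 0.195):

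- r = 0.3: 0.127 lesions
- r = 0.5: 0.212 lesions

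| Starting number and exclusion (studied vs comparator) | r = 0.3 | r = 0.5 |
|---|---|---|
| 100 per arm, 20% vs 10%, no true effect: false superiority (nominal 2.5%) | 4.9% | 7.6% |
| Same case: two-sided error (nominal 5%) | 6.1% | 8.2% |
| 100 per arm, 15% vs 10%, no true effect: false superiority | 3.6% | 4.6% |
| Same case: two-sided error | 5.3% | 5.9% |
| 100 per arm, 10% vs 20%, true difference 1.15: power | 69.0% | 64.1% |
| 90 per arm, 20% vs 10%, no true effect: false superiority | 4.7% | 7.2% |
| 90 per arm, 10% vs 20%, true difference 1.15: power | 64.4% | 59.5% |

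The 90-per-arm rows assume 10% drop-out unrelated to outcome, after which deviators who have W12 counts are removed (72 and 81 kept). Analysing all 90 per arm gives 2.5% false superiority and, if deviators respond fully, 80.0% power.

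A 20,000-run ANCOVA simulation at 90 per arm gives 5.2% and 7.8% false superiority and 63.8% and 58.6% power for the per-protocol set. With all 90 per arm it gives 2.6%, and 79.6% to 79.8%.

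**3. Bounds on the illustration.**

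- Weaker link: at r = 0.1, 100 per arm and 20% vs 10%, false superiority is 3.2% and two-sided error 5.1%.
- Opposite sign: if excluded subjects tend to have good results, the arms swap roles. With 90 per arm, 20% vs 10% and r = −0.3 or −0.5, false superiority falls to 1.2% or 0.7%, and power at a true difference of 1.15 is 64.4% or 59.5%.
- Equal exclusion of similar subjects: 2.5%.
- Part of the power loss is smaller numbers, not bias. With no bias, keeping 90 and 80 gives 77.6%, and keeping 81 and 72 gives 73.1%. That is about two-fifths of each r = 0.3 loss: (84.0 − 77.6)/(84.0 − 69.0) and (80.0 − 73.1)/(80.0 − 64.4).

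**4. Power of an all-randomised analysis if deviators dilute the effect** (dilution assumed):

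| Dilution | Difference | 100 per arm | 90 per arm |
|---|---|---|---|
| 0% | 1.15 | 84.0% | 80.0% |
| 5% | 1.0925 | 80.2% | 75.9% |
| 10% | 1.035 | 75.8% | 71.3% |
| 20% | 0.92 | 65.7% | 61.1% |

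**The case against.** - **The SAP may settle it.** An SAP validated before lock could add a broader efficacy analysis and define deviations. This stands as a limit: the point concerns the supplied text, which commits to no such analysis.
- **The figures are assumed.** No document supports a twofold imbalance in exclusions or r of 0.3 to 0.5, and at r = 0.1 the distortion is small. This is correct. The defect rests on the rule in Section 14.2, and the figures only show what could follow from it.
- **Per protocol can have more power.** Equal 10% exclusion from 90 per arm, with the full effect retained, gives about 76% to 77% (r = 0.1 to 0.3), against 71.3% for all 90 per arm with 10% dilution. This is also correct. It is a reason to report the per-protocol result, but it does not justify resting a superiority claim on that set alone.
- **The remedy may reach few subjects.** Section 9.6 lists "Protocol deviation (after agreement of the Sponsor and/or the investigator") as a withdrawal criterion and plans no follow-up. Section 11.4 lets interfering therapy lead to withdrawal. Section 10.5 does not say that low compliance excludes anyone. Deviators who are withdrawn have no W12 count under either analysis, so this limit stands.
- **The ITT-labelled set would nearly do.** Running the model on that set would answer most of the point, since subjects without a post-baseline count add nothing. It still requires use of both products, and the superiority claim would still rest on per protocol unless the primary set were changed.

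**Conclusion.** The concern holds. In the supplied text, the only planned test of superiority uses a set that can depend on events after randomisation, under exclusion rules not yet written, with no all-randomised result beside it. That reading comes from the text and is firm. The bias is a possibility of unknown size and direction. It arises only if exclusion differs by arm and is linked to outcome. Under the assumed 20% versus 10% exclusion, false superiority runs from 3.2% (r = 0.1) to 7.6% (r = 0.5) against a nominal 2.5%. If the sign of the link is reversed, the test loses power instead. This is a cheap improvement to the plan; nothing here shows that the trial's result would be wrong.

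**What to change.** Amend Section 14.2, and carry the change into the SAP before lock:

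1. Make the primary efficacy set all randomised subjects, analysed as randomised, using all available W4, W8 and W12 counts in the mixed model of Section 14.3.
2. Keep the per-protocol analysis as supportive.
3. Add one sensitivity analysis of the missing-at-random assumption, because withdrawn subjects are not followed up.
4. Report by arm the number of randomised subjects with no post-baseline count, since they add no information to the model.

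The text should state the limit: this restores deviators who stayed in the study, but not the W12 counts of those withdrawn.

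The cost is wording, one more run of the planned model and one sensitivity run. No new visits, subjects or measurements are needed. The downside is dilution by non-adherent subjects. With 10% drop-out, any dilution takes power below the planned 80%, before whatever the W4 and W8 data recover. The documents do not allow that recovery to be calculated.

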10.4. Dosage and application of the IP

At W0, W4 and W8, subjects will be supplied with 1 tube of Epiduo® and 1 of the 2 cosmetic products according to the randomisation for a 4-week application period.

Once-a-day, on the morning, the subjects will apply about one hazelnut of IP (amount equivalent to the amount generally used for a product of this type) to their face (avoiding eyes contour) in place of their usual product.

Once-a-day, on the evening (before bedtime), the subjects will apply the IP “Adapalene 0.1%/ benzoyl peroxide 2.5% treatment” on their face (affected area) on a cleansed and dried skin. The product must be applied in thin layer evenly with fingertips, avoiding eyes, lips and nostrils.

The subjects will have to wash carefully their hands after each application.

All IP applications will be made at home from W0 until the day before the last visit (W12) (i.e. 12-week application period).

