11.7. Adverse events and serious adverse events

11.7.1. Adverse events

11.7.1.1. *Definition of adverse events*

An **adverse event** is any untoward medical occurrence in a subject who has been administered an IP, which does not necessarily have a causal relationship with this IP.

An **Adverse Event** (AE) can therefore be any unfavourable and unintended sign (including an abnormal laboratory finding), symptom, or disease temporally associated with the use of an IP, whether or not related to the IP.

Thus any new sign, symptom or disease, or clinically significant increase in the intensity of an existing sign, symptom or disease, should be considered as an adverse event.

Notes:

- Clinically significant worsening of the disease/condition being evaluated, which occurs during the study, may be considered as an adverse event according to the Dermatologist judgment.
- Lack of efficacy of the IP is not considered an adverse event unless it leads to other unfavourable medical occurrence.
- Any new sign or symptoms suffered by the subject as results of accidental or intentional overdose or misuse of the IP should be reported as an adverse event. The overdose itself is not an adverse event.
- Pregnancy is not per se an adverse event. Any incidents of pregnancy during a study will be reported to the Sponsor immediately by letter to the Sponsor. The Sponsor will advise on the appropriate course of action. The subject will be immediately withdrawn from the study and the pregnancy will be documented as required by the protocol.
- Planned hospitalisation for elective treatment of a pre-existing condition that has not worsened from baseline is not considered an AE.

The expected AE of the drug treatment are listed in the “Résumé des Caractéristiques du Produit” (cf Appendix 4).

11.7.1.2. *Reporting of adverse events*

Events reported by the subject, or observed by the investigator, should be described in the following manner.

The **NATURE** of the event should be described in precise, standard medical terminology (i.e., not necessarily the exact words used by the subject). Where possible, a specific diagnosis should be stated (e.g., allergic contact dermatitis).

TIME OF THE EVENT will be described by the terms:

- Onset date (ie the date the first symptoms were experienced by the subject or the date the AE was discovered)
- End date (or left blank for event not resolved at the end of the follow up).

SERIOUSNESS of the event will be described by the terms:

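### The safety set requires use of both products, so a randomised subject exposed to only one is left out of the adverse-event comparison

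*Combined protocol and SAP*

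**What the plan says.** Section 14.2 defines two populations. Efficacy is evaluated per protocol, "while safety evaluation will be done on" a set labelled Intent-To-Treat, which is defined as "all subjects randomized with at least 1 application of each IP".

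The protocol's own usage settles what IP means here. Under section 10.4, at W0, W4 and W8, "subjects will be supplied with 1 tube of Epiduo® and 1 of the 2 cosmetic products according to the randomisation". Section 10.5 spells it out: "The subjects will record each IP (cosmetic product & drug) application in their daily log". The cosmetic is used in the morning. For the adapalene/benzoyl peroxide gel, section 10.4 says "Once-a-day, on the evening (before bedtime), the subjects will apply the IP".

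Three other places bear on the point:

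- Section 11.7.1.1 defines an adverse event as "any untoward medical occurrence in a subject who has been administered an IP".
- Section 9.6 lists among the withdrawal reasons "any adverse event that the investigator considers it is not in the subject's best interest to continue", and plans no follow-up after withdrawal.
- Section 14.3, under safety analyses, compares the arms by chi-square on the count of subjects with at least one product-related event.

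Section 14 announces a SAP to be validated before database lock. The document contains no separate SAP text that changes this set, and no rule for subjects exposed to a single product.

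**The concern.** A safety set is normally built on exposure, so that anyone who has used a study product and could have been harmed by it is counted. Here the word *each* asks for more: the subject must have used both assigned products. Whether a subject goes on to the second product is decided after randomisation, and intolerance of the first can be the reason it does not happen. The rule can therefore remove exposed subjects because of the kind of event that the safety analysis is meant to count.

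It also sets two parts of the protocol against each other. One application of one product is enough for an event to qualify as an adverse event under section 11.7.1.1, but not enough for the subject who had it to enter the set on which events are compared. The per-protocol set does not fill the gap: it serves efficacy, and it drops major deviations. What is at stake is the adverse-event rate by arm.

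**Working it through.** **Step 1. Who is in the set.** Three products are listed in the synopsis and section 10.1, but no subject receives all three, so *each IP* must mean the two assigned to that subject.

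| Subject, after randomisation | Can have an adverse event (11.7.1.1) | In the safety set (14.2) |
|---|---|---|
| Used both products at least once | Yes | Yes |
| Used only the cosmetic | Yes | No |
| Used only the drug | Yes | No |
| Used neither | No | No |

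The two middle rows are the gap. A subject can fall there by stopping everything after the first use of one product, or by using one product for longer and never the other.

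**Step 2. Inputs for size.** The arm size of 100 is given in section 9.1. It follows from section 14.1: with a difference of 1.15, SD 5.0, R² 0.70, two-sided 5% and 80% power, n = 2 × (1.960 + 0.842)² × 5.0² × (1 − 0.70) / 1.15² = 89.02, so 90 per group. Then 180 / 0.90 = 200. The present point does not depend on that calculation beyond the denominator of 100.

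The plan gives no adverse-event rate and no rate of single-product use. The two remaining inputs are therefore assumptions: *b*, the other subjects in the arm with a related event (5 or 10), and *k*, the reactors excluded from that arm, all with a related event (1, 3 or 5).

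**Step 3. Formula.** The rate among all exposed subjects is (b + k)/100. The rate as analysed under section 14.2 is b/(100 − k). The shortfall is the difference, which equals (k/100) × [1 − b/(100 − k)].

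| b | k | All exposed | As analysed | Shortfall (percentage points) |
|---|---|---|---|---|
| 5 | 1 | 6/100 = 6% | 5/99 = 5.05% | 0.95 |
| 5 | 3 | 8/100 = 8% | 5/97 = 5.15% | 2.85 |
| 5 | 5 | 10/100 = 10% | 5/95 = 5.26% | 4.74 |
| 10 | 1 | 11/100 = 11% | 10/99 = 10.10% | 0.90 |
| 10 | 3 | 13/100 = 13% | 10/97 = 10.31% | 2.69 |
| 10 | 5 | 15/100 = 15% | 10/95 = 10.53% | 4.47 |

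Each excluded reactor lowers the arm's analysed rate by about 0.9 to 1.0 percentage point. The rows with k = 3 and k = 5 show how the shortfall scales; they are not forecasts.

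**Step 4. Which arm.** Section 10.4 has applications start at W0 but does not say which product comes first. Exclusion criterion 15 in section 9.3 bars topical products on the face on the day of inclusion, which is compatible with the drug being used first, that evening. Section 11.3 bars IP on the face on visit days, which could be read as putting the cosmetic first, the next morning. If the drug comes first, losses before any cosmetic use should be roughly balanced, because the drug is common to both arms. If the cosmetic comes first, losses could differ by arm. The text does not decide between the two.

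**The case against.** The best case against the point is that it affects almost nobody. With one product in the morning and the other in the evening, a subject who follows the schedule is lost only by giving up both products between two applications, normally within a day. A subject who reacts but later uses the other product once stays in, so it would be too strong to say that the set is conditioned on tolerating the first application. This stands, and it limits the size of the point. It does not supply a reason for *each*.

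A reader might infer that the local tolerance comparison is biased. The documents give little support for that. Signs are scored at W0, W4, W8 and W12 and overall tolerance at W12 only (section 11.6.2.3), and no follow-up is planned after withdrawal (section 9.6). A subject who leaves within a day has no scheduled post-baseline score to lose. Only someone who stayed in the study on a single product would have such scores.

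A reader might also infer that a large share of events would be hidden. Assuming 3 to 5 affected subjects in an arm and one or two of them lost gives 1/5 = 20% to 2/3 = 67%. Those counts are assumed, and the top figure pairs the fewest events with the most losses. Nor are the events hidden: all go into the CRF (section 11.6.2.6), serious ones are reported from consent onward (section 11.7.2.2), and withdrawals are summarised by product group and by reason (section 14.3).

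Finally, the comparison in section 14.3 concerns events related to the study product. If that means the cosmetic alone, a subject who used only the drug could add to the denominator but not to the events. The section does not say which meaning applies.

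**Conclusion.** The point holds as a defect in the definition of the set. As written, section 14.2 drops exposed, randomised subjects from the adverse-event comparison because of a post-randomisation event that intolerance can cause, and this is at odds with the protocol's own definition of an adverse event.

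The practical effect is probably small. It is about 1 percentage point of an arm's rate for each excluded reactor, on the assumptions of 100 per arm, 5 to 10 other affected subjects, and every excluded subject having a related event that counts in the comparison. How many would be excluded cannot be derived from the documents.

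A claim that the rule favours one arm is not supported, because the order of first use is not stated. The Intent-To-Treat label does not suit a set conditional on exposure to both products, but that is a matter of naming: the set is defined in the same sentence. The change is worth making because the rule is wrong in principle and easily corrected, not because a large distortion has been shown.

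**What to change.** In section 14.2 and the SAP, define the safety set as all randomised subjects with at least one application of any IP (cosmetic or drug), analysed by product received, and call it the safety set rather than ITT. Because a subject who used only the drug has used neither cosmetic, add that such a subject is counted under the cosmetic dispensed.

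The cost is one or two sentences, to be settled before the SAP is validated and the database locked. Sample size, visits, data collection and handling of subjects do not change; product use is already recorded in the daily log under section 10.5.
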